MDE	major depressive episode
MedDRA®	Medical Dictionary for Regulatory Activities
MINI	Mini International Neuropsychiatric Interview
mITT	Modified Intent-to-treat
MMRM	Mixed-effect Model for Repeated Measures
msec	Millisecond
PCS	Potentially Clinically Significant
PET	Positron Emission Tomography
QTcB	corrected QT Interval Using the Bazett Formula
QTcF	corrected QT Interval Using the Fridericia Formula
SAE	serious adverse event
SAS	Simpson Angus Scale
SERT	serotonin transporter
SAP	Statistical Analysis Plan
TEAE	treatment-emergent adverse event
TOEP	Toeplitz Structure
TOEPH	Heterogeneous Toeplitz Structure
ULN	upper limit of normal
US	United States
YMRS	Young Mania Rating Scale

1 PROTOCOL SYNOPSIS AND SCHEDULE OF EVENTS

- Title:A Phase 3, Randomized, Double-Blind, Placebo-Controlled,
Multi-Center Study to Assess the Efficacy and Safety of
Lumateperone Monotherapy in the Treatment of Patients with
Major Depressive Episodes Associated with Bipolar I or
Bipolar II Disorder (Bipolar Depression) or Major Depressive
Disorder
- Study Design: This is a Phase 3, randomized, double-blind, placebo-controlled, multicenter study to evaluate the efficacy and safety of lumateperone monotherapy in the treatment of patients with major depressive episodes (MDEs) associated with Bipolar I or Bipolar II Disorder (Bipolar Depression) or major depressive disorder (MDD) who also meet the Diagnostic and Statistical Manual of Mental Disorder, 5th Edition (DSM-5) criteria for mixed-features. The study consists of a Screening Period, a Double-blind Treatment Period, and a Safety Follow-up Period.

Screening Period (2 Weeks)

Potential patients will be evaluated during a Screening Period lasting up to 2 weeks.

After obtaining written informed consent, diagnostic interviews and physical examinations will be conducted, vital signs and ECGs will be assessed, and blood samples for laboratory assessments will be collected. Patients considered potentially eligible for participation will be required to discontinue their current antidepressant treatment and/or other psychotropic drugs.

At Baseline (Visit 2), patients who continue to meet all eligibility criteria will be randomly assigned in a 1:1 ratio to 1 of the 2 treatment arms (lumateperone 42 mg or placebo) for a 6-week, double-blind treatment period.

Double-blind Treatment Period (6 Weeks)

1

Patients will take their first dose of study drug the evening of their randomization visit. A single dose will be taken each day in the evening for the duration of the on-treatment period. Following randomization, patients will attend clinic visits on Days 8, 15, 22, 29, 36, and 43.

The Double-blind Treatment Period will be a total of 6 weeks.

Safety Follow-up Period (2 Weeks)

A return to the clinic for a safety follow-up visit will occur at Week 8, approximately 2 weeks following the last dose of study drug. Patients who withdraw prematurely should be seen for an early termination visit and will be asked to return to the clinic for a safety follow-up visit approximately 2 weeks after Visit 8/Early Termination (ET).

Objectives: Primary Objective:

The primary objective of this study is to confirm the efficacy of lumateperone 42 mg administered orally once daily compared with that of placebo as measured by mean change from baseline to Day 43 in the Montgomery-Åsberg Depression Rating Scale (MADRS) total score in patients with bipolar depression with mixed features or MDD with mixed features.

Secondary Objectives

Key Secondary Objective:

The key secondary objective of this study is to confirm the efficacy of lumateperone 42 mg administered orally once daily compared with that of placebo as measured by mean change from baseline to Day 43 in Clinical Global Impression Scale–Severity (CGI-S) score in patients with bipolar depression with mixed features or MDD with mixed features.

Safety Objective:

The safety objective of this study is to determine the safety and tolerability of lumateperone administered orally once daily compared with that of placebo in patients with bipolar depression or MDD as assessed by adverse events (AEs); vital clinical laboratory results; sign measures; electrocardiogram (ECG) results; suicidality as assessed by the Columbia-Suicide Severity Rating Scale (C-SSRS); manic symptoms as assessed by the Young Mania Rating Scale (YMRS); and extrapyramidal symptoms (EPS) as assessed by Abnormal Involuntary Movement Scale (AIMS), Barnes Akathisia Rating Scale (BARS), and Simpson Angus Scale (SAS) scales.

Population:	Male and female patients between the ages of 18 and 75 years, inclusive, with a diagnosis of Bipolar I or Bipolar II Disorder with mixed features or major depressive disorder (MDD) with mixed features who are experiencing a major depressive episode (MDE) and who meet the following criteria may be eligible for participation in the study:		
	 The start of the current MDE is at least 2 weeks but no more than 6 months prior to Screening (Visit 1); 		
	 The patient has at least moderate severity of illness as measured by MADRS total score ≥ 24 and CGI-S score ≥ 4 at Screening (Visit 1) and Baseline (Visit 2); 		
	• The patient has sufficient history and/or independent report verifying that the current MDE is causing clinically significant distress or impairment in social, occupational, or other important areas of functioning;		
	• The patient has a YMRS total score between 4 and 16, inclusive, at Screening (Visit 1) and Baseline (Visit 2).		
	Patients will be enrolled in multiple countries globally.		
Phase:	3		
Number of Sites:	Up to 60 sites, approximately		
Description of Intervention:	Patients will be randomized to receive either lumateperone 42 mg or placebo. Patients will self-administer doses orally, once daily, each evening at home for the duration of the Double- blind Treatment Period. Study drug will be provided in blister cards containing capsules, and patients will be instructed to take 1 capsule per dose.		
Study Duration:	For each patient completing the study, the study will last up to approximately 10 weeks (9 visits), including a Screening Period, a Double-blind Treatment Period, and a Safety Follow-up Period.		
Statistical	Efficacy Analyses		
Methods:	The primary efficacy endpoint is the change from baseline to Day 43 in MADRS total score.		
	The analysis of the primary efficacy endpoint will be performed using a mixed-effects model for repeated measures (MMRM) with the change from baseline in the MADRS total score at each pre-specified postbaseline time point as the response variable; treatment group, visit, site (or pooled site), the stratification factor at screening (Bipolar Disorder or MDD diagnosis), and treatment group-by-visit interaction as factors; and the baseline		

MADRS total score and visit-by-baseline MADRS total score interaction as covariates. An unstructured covariance matrix will be used to estimate the covariance among repeated measurements within patient. This analysis will be performed based on all post-baseline scores using only the observed cases without imputation of missing values. This primary efficacy analysis will first be performed based on the combined patient population of Bipolar Disorder with mixed features and of MDD with mixed features. If this primary analysis based on the combined population is statistically significant at 0.05 level, then by using a similar MMRM model the primary efficacy analyses will be performed separately for the subpopulation of Bipolar Disorder with mixed features.

The key secondary efficacy endpoint is the change from baseline to Day 43 in CGI-S score. This endpoint will be analyzed using an MMRM model similar to the one proposed for the analysis of the primary efficacy endpoint replacing MADRS total score with CGI-S score for the baseline and baseline-byvisit interaction terms as covariates in the model. The key secondary efficacy analysis will first be performed based on the combined patient population of Bipolar Disorder with mixed features and of MDD with mixed features. If the key secondary analysis is statistically significant at 0.05 level, then by using a similar MMRM model, the key secondary efficacy analyses will be performed separately for the subpopulation of Bipolar Disorder with mixed features and for the subpopulation of MDD with mixed features.

Multiple comparisons for the primary and key secondary efficacy endpoints will be addressed using a fixed-sequence (hierarchical) gatekeeping strategy combined with Hochberg procedure. The key secondary efficacy endpoint will be tested and its 2-sided p-value compared with 0.05 level for statistical significance only if the comparison for the primary efficacy endpoint is significant for the combined and two separate subpopulations at 2-sided $\alpha = 0.05$ overall level. Otherwise, the p-value for the key secondary efficacy endpoint will be reported as nominal.

The efficacy conclusion will be based on the analyses using the modified Intent-to-Treat (mITT) Analysis Set. The mITT Analysis Set is defined as all randomized patients enrolled after the implementation of Amendment 2.0 (dated 02 Nov 2020) who received at least 1 dose of study drug and had baseline and at least 1 post-baseline assessment of MADRS total score.

Descriptive analyses of the efficacy endpoints will be performed for patients enrolled before the implementation of Amendment 2.0 (dated 02 Nov 2020).

Safety Analyses

Safety data such as reported and observed AEs and SAEs, clinical laboratory results, vital signs, physical and neurological examination findings, ECGs, YMRS, EPS as measured by AIMS, BARS, and SAS, and C-SSRS, will be summarized descriptively by treatment group and visit. When appropriate, out-of-range values will be flagged in data listings and tabulated. Shift tables will be prepared for pre-specified safety measures.

The safety analysis will be performed using the Safety Analysis Set, defined as all randomized patients who received at least 1 dose of study drug.

A statistical analysis plan (SAP) will be finalized prior to unblinding patients' treatment assignments.

Sample Size: The assumed effect size (treatment-group difference relative to pooled standard deviation) of 0.37 for lumateperone is based on a treatment difference of 3.3 units with a common pooled standard deviation of 9 for the primary efficacy parameter, change from baseline to Day 43 in MADRS total score. A sample size of 350 patients (175 per treatment group) enrolled after the implementation of Amendment 2.0 (dated 02 Nov 2020) will be needed to provide 90% power for primary analysis for the combined population of Bipolar Disorder with mixed features and MDD with mixed features based on a mixed-effect model for repeated measures (MMRM) using simulation method (Lu, 2012). The simulation assumes a correlation of 0.7 between the repeated measures and a dropout rate of 10% based on historical data.

The sample size and statistical power for the primary analyses in the subpopulations are presented in Section 9.1.

The study randomized approximately 100 patients under the original protocol before the implementation of Amendment 2.0 (dated 02 Nov 2020); therefore, the total enrollment for the study will be approximately 450 patients.

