3 STUDY OBJECTIVES

3.1 Primary Efficacy Objective

The primary objective of this study is to confirm the efficacy of lumateperone 42 mg administered orally once daily compared with that of placebo as measured by mean change from baseline to Day 43 in the MADRS total score in patients with bipolar depression with mixed features or MDD with mixed features.

This study will evaluate the efficacy of lumateperone 42 mg based on the following three sets of patients:

- 1. All patients enrolled after the implementation of Amendment 2.0, which includes all patients associated with Bipolar Depression with mixed features and all patients associated with MDD with mixed features;
- 2. All patients with Bipolar Disorder (I or II) with mixed features enrolled after the implementation of Amendment 2.0;
- 3. All patients associated with MDD with mixed features.

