9 STATISTICAL CONSIDERATIONS

A statistical analysis plan (SAP) will be finalized prior to unblinding the patients' treatment assignments and will provide further details regarding the definition of analysis endpoints and analysis methodology to address all study objectives. Changes made to the data analysis methods as described in the protocol will be documented in the SAP and will not necessitate a protocol amendment. All departures from the statistical analyses described in the approved protocol, whether made before or after unblinding, will be documented, and justified in the final clinical study report.

The study randomized 100 patients with Bipolar Disorder (Bipolar I or Bipolar II) before Amendment 2.0 (dated 02 Nov 2020). The efficacy data of these 100 patients will be combined with those of patients with Bipolar Disorder enrolled after Amendment 2.0 as a separate analysis.

Table 9-1 presents an overview of the statistical data analyses planned for all patients enrolled in the study.

Table 9-1: Overview of Statistical Data Analyses

	Patients	Patients Randomized after Protocol Amendment 2.0			All Bipolar Patients	All Patients
Analysis	Randomized before Protocol Amendment 2.0	Bipolar Disorder with Mixed Features	MDD with Mixed Features	All Patients Randomized after Protocol Amendment 2.0	(randomized before or after Amendment 2.0)	randomized before or after Amendment 2.0
Patient Disposition	Yes	Yes	Yes	Yes	Yes	Yes
Protocol Deviation	Yes	Yes	Yes	Yes		Yes
Demographic and baseline characteristics	Yes	Yes	Yes	Yes	Yes	Yes
Bipolar Diagnosis, Psychiatric Diagnosis and History	Yes	Yes	Yes	Yes	_	_
Medical History	Yes	Yes	Yes	Yes	—	—
Prior/Concomitant Medication	Yes	Yes	Yes	Yes	—	_
Exposure/ Compliance	Yes	Yes	Yes	Yes	Yes	Yes
Primary and Key Secondary Efficacy	Yes ¹	Yes	Yes	Yes	Yes	Yes
AE	Yes	Yes	Yes	Yes	Yes	Yes
Labs	—	Yes	Yes	Yes	Yes	Yes
Vital Signs		Yes	Yes	Yes	Yes	Yes
ECG	_	Yes	Yes	Yes	Yes	Yes
C-SSRS		Yes	Yes	Yes	Yes	Yes
YMRS	Yes	Yes	Yes	Yes	Yes	Yes
AIMS, BARS, and SAS ²		Yes	Yes	Yes	Yes	—

AE = adverse event; AIMS = Abnormal Involuntary Movement Scale; BARS = Barnes Akathisia Rating Scale; C-SSRS = Columbia Suicide Severity Rating Scale; ECG = electrocardiogram; SAS = Simpson-Angus Scale; YMRS = Young Mania Rating Scale.

¹ Descriptive statistics only.

² AIMS, BARS, and SAS assessments were added after implementation of Protocol Amendment 2.0.

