9.1 Sample Size Considerations

The assumed effect size (treatment group difference relative to pooled SD) of 0.37 for lumateperone is based on a treatment difference of 3.3 units with a common pooled SD of 9 for the primary efficacy parameter, change from baseline to Day 43 in MADRS total score. A sample size of 350 patients (175 per treatment group) will need to be enrolled after the implementation of Amendment 2.0 (dated 02 Nov 2020) to provide 90% power for primary analysis for the combined population of Bipolar Disorder with mixed features and MDD with mixed features based on an MMRM model using simulation method (Lu, 2012). The simulation assumed a correlation of 0.7 between the repeated measures and a dropout rate of 10% based on historical data.

The assumed values of drop-out rate of 10%, correlation of 0.7, and standard deviation of 9 are approximate estimates from a previous successful study of lumateperone for bipolar depression. The assumed treatment difference of 3.3 used to obtain the power of 90% is considered appropriate as the generated sample size can cover a wide range of clinically relevant treatment difference to be detected as statistically significant.

The study will enroll approximately equal number of patients (175) for the Bipolar Disorder with mixed features and for MDD with mixed features following Amendment 2.0. Assuming an effect size of 0.45, and same assumptions of drop-out rate and correlation between the repeated measures, this sample size (approximately 87 patients in each treatment group) for each of the two subpopulations is expected to provide approximately 80% statistical power for the primary efficacy analysis with the adjustment of multiplicity for the testing of the primary analysis in each of the subpopulations.

The study randomized approximately 100 patients under the original protocol before the implementation of Amendment 2.0 (dated 02 Nov 2020); therefore, the total enrollment for the study will be approximately 450 patients.

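### Optional efficiency gain: once the combined MADRS test passes at 0.05, Hochberg across the bipolar and MDD tests is not needed to hold the 0.05 family-wise error

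*Protocol*

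**What the plan says.** The Protocol synopsis (Statistical Methods) tests MADRS first in the combined population. The subpopulation analyses follow on a condition: "If this primary analysis based on the combined population is statistically significant at 0.05 level". On multiplicity it says: "Multiple comparisons for the primary and key secondary efficacy endpoints will be addressed using a fixed-sequence (hierarchical) gatekeeping strategy combined with Hochberg procedure". CGI-S is tested "only if the comparison for the primary efficacy endpoint is significant for the combined and two separate subpopulations".

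Protocol 3.1 describes the combined set as one "which includes all patients associated with Bipolar Depression with mixed features and all patients associated with MDD with mixed features". Protocol 9.4.4 applies the primary model to both subpopulations within the mITT set. Protocol 9.1 gives the split: "The study will enroll approximately equal number of patients (175) for the Bipolar Disorder with mixed features and for MDD with mixed features". It adds that about 87 patients per arm in each, at an effect size of 0.45, "is expected to provide approximately 80% statistical power for the primary efficacy analysis with the adjustment of multiplicity".

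The visible SAP repeats the models but contains no multiplicity rule. Its Section 15 records no departures from the protocol.

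**The concern.** On this reading, a subpopulation that succeeds alone must reach p≤0.025, because Hochberg allows 0.05 only when both succeed. A subpopulation with p between 0.025 and 0.05 is therefore declared negative whenever the other misses 0.05. If the combined gate already controls the family-wise error, that stricter threshold gives up valid claims that the 0.05 limit does not require the trial to give up. What is at stake is a lone bipolar or lone MDD claim. The combined claim and the route to CGI-S are not affected.

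**Working it through.** **1. Inputs (Protocol 9.1 unless noted).** Subpopulation effect size 0.45; about 87 per arm in each; dropout 10%; correlation 0.7; combined difference 3.3 with SD 9; 175 per arm combined. The gate is two-sided 0.05 (synopsis).

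**2. Effective size per arm.** If all dropouts are lost, n = 87 × 0.9 = 78.3. If none are lost, n = 87. For an MMRM with compound-symmetric correlation ρ = 0.7 and all dropouts leaving after visit k, the Day 43 mean has effective size 87 / [R² + (1 − R²)/0.9], with R² = kρ²/(1 + (k − 1)ρ).
- k = 1: R² = 0.49, n = 82.3.
- k = 5: R² = 2.45/3.8 = 0.645, n = 83.7.
- Dropout spread evenly over visits (an assumed pattern): n = 83.2.

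**3. The plan's own figures.** Combined, with 175 × 0.9 = 157.5 per arm, power is 90.2% at 3.3/9 and 90.7% at 0.37, which matches the stated 90%. For one subpopulation at n = 78.3, the mean of z is 0.45 × √(78.3/2) = 2.816. This gives:
- P(p≤0.05) = Φ(2.816 − 1.960) = 80.4%
- P(p≤0.025) = Φ(2.816 − 2.241) = 71.7%
- Hochberg before the gate: 0.717 + (0.804 − 0.717) × 0.804 = 78.7%
- Hochberg after the gate, whose own power is 97.8%: 78.6%

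At n = 83.2 the same calculation gives 81.2%. The stated figure of about 80% is reproduced.

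**4. Why the gate is enough.** The combined effect is a weighted average of the two subpopulation effects.
- Both subpopulation nulls true: the combined null is also true, so any false claim must first pass a 0.05 test of a true null.
- Exactly one subpopulation null true: its own 0.05 test bounds the error.
- Opposite effects that cancel: the only true null is the combined one, tested at 0.05.

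This is a closed test with the combined test as the intersection test.

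**5. Power.** The bipolar and MDD z-statistics are independent normal with mean d√(n/2), and the combined z is their information-weighted sum. Before the gate, the gain from dropping Hochberg is P(0.025 < p ≤ 0.05) × P(other p > 0.05). At n = 78.3 that is 0.087 × 0.196 = 1.7 points. With the gate (4 million simulated trials, results favouring lumateperone):

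| Effect in both | n per arm | Hochberg | Full 0.05 | Gain (points) | Both won, either rule | Lone claim lost, all trials |
|---|---|---|---|---|---|---|
| 0.45 | 78.3 | 78.6% | 80.1% | 1.6 | 64.6% | 3.1% |
| 0.45 | 83.2 | 81.2% | 82.5% | 1.3 | 68.4% | 2.6% |
| 0.45 | 87 | 83.1% | 84.2% | 1.1 | 71.1% | 2.2% |
| 3.3/9 | 78.3 | 58.5% | 62.0% | 3.5 | 39.8% | 7.0% |
| 3.3/9 | 83.2 | 61.6% | 64.8% | 3.2 | 43.2% | 6.5% |
| 3.3/9 | 87 | 63.8% | 66.8% | 3.0 | 45.8% | 6.0% |

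Gains are taken from unrounded values. Winning both is identical because each rule declares both significant exactly when both p-values are at most 0.05. Among trials that pass the gate with exactly one p≤0.05, the lone claim is lost in 8.5 to 10.0% at 0.45 and 14.4 to 15.8% at 3.3/9.

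The chance of at least one subpopulation claim is 2 × (power of one) − (both won). At n = 78.3 and 0.45 it rises from 92.5% to 95.6%.

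**6. Family-wise error, combined test included (78.3 per arm, Hochberg vs none).**
- No effect in either: 0.050 vs 0.050
- One null, 3.3/9 in the other: 0.020 vs 0.024
- One null, 0.45 in the other: 0.023 vs 0.025
- One null, effect size 3 in the other: 0.050 vs 0.050
- Opposite effects of 0.3: 0.050 vs 0.050

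An unequal split (105 and 52 per arm, times 0.9) without Hochberg also stays at or below 0.050. When both nulls are true, the chance of any false subpopulation claim rises from 2.1% to 3.3%.

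**The case against.** The strongest reply is that nothing is wrong: Hochberg is standard and valid, and a sponsor may prefer a stricter threshold for a lone claim drawn from half the trial. That is fair, and it is why the change is optional.

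The exact Hochberg rule is also inferred. The synopsis names only the bipolar subpopulation after the gate, and the stated 80% fits either rule (78.6% and 81.2% with Hochberg, 80.1% without at 78.3 per arm). This stands as a caveat. Still, Protocol 9.1 and 9.4.4 refer to both subpopulations, and these are the only parallel primary tests shown.

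The gain is small. Uncertainty about effective size alone moves Hochberg power by 4.5 points (78.6 to 83.1%). There is also a price beyond the both-null case: with one null and an assumed 0.20 in the other, false claims rise from 1.5% to 2.1% at 87 per arm. Both points are true, and the price stays within 0.05.

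Finally, Hochberg would protect the subpopulation claims even if the combined model were miscalibrated. With neither the gate nor Hochberg, the error under both nulls would be 1 − 0.95² = 0.0975. No miscalibration has been quantified, and it would damage the combined claim under either rule.

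**Conclusion.** The point holds as an optional improvement; the current plan is valid and delivers about its stated power. Testing each subpopulation at 0.05 after the gate is never less powerful than Hochberg and keeps the same 0.05 maximum family-wise error. The gain is 1.1 to 1.6 points per subpopulation at 0.45. It is 3.0 to 3.5 points if both have only the 3.3/9 assumed for the combined test. That sensitivity case is reasonable, since 0.45 in both halves would imply about 0.45 combined, not 0.37.

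The conclusion rests on four conditions: Hochberg applies across the two subpopulations; the gate stays at two-sided 0.05; all tests use the same mITT set; and the normal approximation is adequate. Confidence is medium, because the detailed multiplicity text is not public.

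**What to change.** Before unblinding, state in the SAP that once the combined MADRS test is significant at two-sided 0.05, each subpopulation is tested at two-sided 0.05 without Hochberg. Add the short error-control argument and list the change in Section 15. Keep the rule that all three MADRS tests must be significant before CGI-S. If Hochberg is also used within CGI-S, which the public text does not show, the same rule can apply there. If the full multiplicity text uses Hochberg differently, recheck the argument first.

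The cost is SAP text only, with no extra patients or data. Protocol Section 9 says changes to the analysis methods "will be documented in the SAP and will not necessitate a protocol amendment", but departures, "whether made before or after unblinding, will be documented, and justified in the final clinical study report". The sponsor must therefore justify and date a relaxed confirmatory threshold, and accept that a lone subpopulation claim may rest on p up to 0.05 instead of 0.025.

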3.2 Secondary Efficacy Objectives

3.2.1 Key Secondary Efficacy Objective

Following Protocol Amendment 2.0, the key secondary efficacy objective of this study is to confirm the efficacy of lumateperone 42 mg administered orally once daily compared with that of placebo as measured by mean change from baseline to Day 43 in the Clinical Global Impression Scale-Severity (CGI-S) score in patients with MDEs associated with bipolar depression with mixed features or associated with MDD with mixed features.

The key secondary efficacy objective will be assessed using the same three sets of patients defined for the primary efficacy objective.

4. ANALYSIS SETS

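### Is it a flaw that CGI-S is formally tested only after MADRS has won in the combined population and in both diagnoses?

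*Protocol*

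**What the plan says.** The Statistical Methods part of the protocol synopsis sets the order of testing. MADRS is tested first in the combined population. "If this primary analysis based on the combined population is statistically significant at 0.05 level", testing moves to the subpopulations. Multiplicity over the primary and key secondary endpoints is handled "using a fixed-sequence (hierarchical) gatekeeping strategy combined with Hochberg procedure". CGI-S is then tested at two-sided 0.05 "only if the comparison for the primary efficacy endpoint is significant for the combined and two separate subpopulations". "Otherwise, the p-value for the key secondary efficacy endpoint will be reported as nominal".

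The rank of each claim is set elsewhere. Protocol 3.1 and SAP 3.1 both place three patient sets under the primary efficacy objective: everyone enrolled after Amendment 2.0, the bipolar patients, and the MDD patients. CGI-S comes under the key secondary objective. The synopsis says: "The key secondary objective of this study is to confirm the efficacy of lumateperone 42 mg". SAP 3.2.1 adds: "The key secondary efficacy objective will be assessed using the same three sets of patients".

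Protocol 9.1 gives 90% power for combined MADRS (difference 3.3, SD 9, 175 per arm). For each subpopulation, about 87 per arm, it plans differently: "Assuming an effect size of 0.45, and same assumptions of drop-out rate and correlation between the repeated measures", the result is "approximately 80% statistical power for the primary efficacy analysis with the adjustment of multiplicity". It does not give the probability of winning in both subpopulations.

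**The concern.** The event that admits CGI-S is not one of the events for which power is stated. A reader who sees 90% and about 80% may expect CGI-S to be tested almost whenever the trial succeeds. In fact two independent half-size tests must both succeed, and the chance of that is roughly the square of one subpopulation's power. Even the CGI-S comparison in all 350 patients waits for this. Hochberg also allows a claim in one diagnosis alone, and CGI-S then stays nominal.

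At stake would be an objective worded as confirmation that often could not be confirmed, even with a real CGI-S effect and a significant combined MADRS result. An alternative exists that also controls error: once combined MADRS is significant, give CGI-S a share of alpha at once. If the present rule were needlessly strict, changing it would cost a few sentences and no patients.

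**Working it through.** **Inputs.** From Protocol 9.1: difference 3.3, SD 9 (d = 3.3/9 = 0.3667); 175 per arm combined; 175 patients, so 87.5 per arm, in each diagnosis; d = 0.45 for the subpopulations; 10% dropout. Two-sided 0.05 is from Protocol 9.4. The effective fraction f is taken as 0.90 (completers only) to 1.0 (no loss); MMRM with correlation 0.7 lies between.

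**Formula.** θ = d × √(n·f/2); power = Φ(θ − 1.96).

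**The plan's own figures.**

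- Combined, f = 0.90: θ = 0.3667 × √(157.5/2) = 3.254, power Φ(1.294) = 0.902. With f = 1.0 it is 0.929. The stated 90% reproduces.
- Subpopulation at 0.45, f = 0.90: θ = 0.45 × √(78.75/2) = 2.824, so power is 0.806 at 0.05 and 0.720 at 0.025. Hochberg gives 0.720 + (0.806 − 0.720) × 0.806 = 0.789, or 0.788 once combined significance is also required. With f = 1.0 the latter is 0.833. The stated figure of about 80% reproduces.

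**Chance that CGI-S is formally tested.** With two hypotheses, Hochberg rejects both exactly when both p-values are at most 0.05. The diagnoses contain different patients, so the probability is the square of subpopulation power at 0.05. The combined test adds no further loss: if both z-values exceed 1.96, the combined z is at least 2 × 1.96/√2 = 2.77.

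| MADRS d in each diagnosis | f | θ | Power at 0.05 | Both win |
|---|---|---|---|---|
| 0.45 | 0.90 | 2.824 | 0.806 | 0.650 |
| 0.45 | 1.0 | 2.976 | 0.845 | 0.714 |
| 0.3667 | 0.90 | 2.301 | 0.633 | 0.401 |
| 0.3667 | 1.0 | 2.425 | 0.679 | 0.461 |

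The first two rows are the protocol's planning case for the subpopulations. The last two carry the combined assumption into each half, which the protocol does not do.

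**Error control.** Combined MADRS is tested at 0.05, then Hochberg is applied at 0.05 to the two subpopulations, and CGI-S is tested at 0.05 only if everything before it is rejected. In simulation over 14 null configurations and 4 correlations, the largest one-sided family error was 0.0252 against 0.025, within simulation error. The alternative below gave the same value. The two schemes differ in power, not validity.

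**What the alternative buys and costs.** Take combined MADRS at 0.05; then combined CGI-S at 0.01 alongside Hochberg at 0.04 for the subpopulations, each side passing its alpha on if it wins. The documents give no CGI-S effect and no MADRS/CGI-S correlation, so both are assumed (correlation 0.5 and 0.8). With MADRS at 0.45 in both diagnoses:

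| Assumed CGI-S effect | Formal CGI-S success, plan | With split | Largest loss of MADRS power per subpopulation (points) |
|---|---|---|---|
| 0.45 | 65–71% | 92–95% | 0.3 |
| 0.37 | 62–70% | 80–86% | 1.2 |
| 0.30 | 55–65% | 65–72% | 2.0 |
| 0.20 | gain of only 0.3–2.3 points | | 2–3 |
| 0 | no gain | | 2.9 (0.788 to 0.759) |

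In the last row with f = 0.90, the chance of winning MADRS in both diagnoses falls from 0.650 to 0.607.

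Setting a 40 to 46% chance of being tested against 90 to 99% therefore overstates the contrast. The second range pools two scenarios, and it counts a test that begins at 0.01 as equal to one at 0.05.

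**The case for a change.** The best case for the concern is this. Even at 0.45, about three trials in ten cannot test CGI-S formally. Exactly one diagnosis wins in 24 to 28% of trials (36 to 37% at 3.3/9). A closed path is plausible: Protocol 2.1 describes lumateperone efficacy trials in bipolar depression, while Protocol 2.2 supports the MDD arm from other D2 antagonists. If MADRS is 3.3/9 in each half and CGI-S has the same standardised effect, the split raises formal CGI-S success from 39–46% to 74–80% for about one point of subpopulation power. Protocol 9 lets the SAP change methods before unblinding.

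All of that arithmetic stands, and a sponsor who valued CGI-S in the combined population above the separate diagnosis claims could reasonably choose the split. It does not make the present order wrong. CGI-S goes untested because MADRS missed in at least one diagnosis, and that is evidence on the primary objective. SAP 9.2 still reports the CGI-S difference, confidence interval and p-value; only the confirmatory label is lost. The split also leaves CGI-S within each diagnosis behind the same both-win condition, so two of the three sets in SAP 3.2.1 gain nothing.

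It is also true that Protocol 9.1 omits the both-win probability. Stating it would help a reader, but it would change no test, estimate or conclusion.

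**Conclusion.** The concern does not hold. The rule puts a secondary endpoint after a primary family that both documents define over three patient sets. It controls the error rate and is consistent with every power figure given. Its price is that CGI-S is formally tested in 65 to 71% of trials at the protocol's subpopulation effect size, or 40 to 46% if each diagnosis shows only 3.3/9. Relaxing it would move alpha from two primary claims to a secondary one, for a benefit that ranges from large to negligible over CGI-S effects the documents do not specify. Reasonable statisticians would differ on that trade.

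This rests on normal approximations, independent diagnoses of equal size, and effective fractions of 0.90 to 1.0. It also rests on the synopsis for the testing order, since fuller multiplicity text may be withheld from the public copy. The synopsis sentence on the follow-on MADRS test names only the bipolar subpopulation. Reading it as both diagnoses follows the multiplicity paragraph and agrees with Protocol 3.1, 9.1 and 9.4.4.
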